### 8.5.2 Analysis of other endpoints

(1) Changes in mean Hb values from the first day of the treatment period at Weeks 20 and 24 of the treatment period

Descriptive statistics for change from Hb value on the first day of the treatment period to mean Hb values at Week 20 and Week 24 in the treatment period should be calculated. A paired t-test should be performed for before and after comparison of changes from the first day of the treatment period.

LSMean, its standard errors, and 2-sided 95% CI for change from Hb value on the first day of the treatment period to mean Hb values at Week 20 and Week 24 in the treatment period should be calculated using the MMRM model (with compound symmetry [CS] for a covariance matrix within subject variance).

Only the Conversion (Hb value  $< 11.0$  g/dL) cohort will be analyzed.

(2) Proportion of subjects with a  $\geq 1.0$  g/dL increase in mean Hb values from the first day of the treatment period at each time point of the treatment-period.

The number and proportion of subjects and 95% CI (Clopper-Pearson [exact] method) for the proportion of subjects with a mean Hb value increase of  $\geq 1.0$  g/dL from the first day to each evaluation time point of the treatment period should be provided. Only the Conversion (Hb value  $< 11.0$  g/dL) cohort will be analyzed.

(3) Proportion of subjects who received rescue therapy with ESA formulations, blood transfusion, or phlebotomy

The number and proportion of subjects and the 95% confidence interval (Clopper-Pearson [Exact] method) for the proportion of subjects receiving rescue therapy with an ESA preparation should be provided, after the first day of the treatment period, in each period between scheduled study visits and during the entire treatment period from the first day to Week 24 of the treatment period.

The analyses same to the above subjects receiving rescue therapy with ESA formulation should be performed for subjects receiving rescue therapy with RBC transfusion or receiving phlebotomy.

(4) Study drug dosage

## 1) Study drug dosage

Descriptive statistics of mean daily dose should be calculated for each scheduled study visit from the first day of the treatment period up to treatment period Week 24. The time course diagram for mean daily dose should be separately prepared. The 95% CI of the mean will be represented by an error bar. Each period between scheduled study visits is defined as the period between the scheduled study visit and the day before the next scheduled study visit.

## 2) Distribution of dosage of MT-6548 tablets:

The number, proportion, and 95% CI (Clopper-Pearson [Exact] method) for the proportion of subjects per daily dose based on the prescription should be provided at each evaluation time point up to Week 20 of the treatment period after the first day of the treatment period.

Proportion of subjects per dose based on the prescription at each evaluation time point from the first day of the treatment period to Week 20 of the treatment period should be as a stacked bar graph with the number of subjects at each evaluation time point as 100%. Stacked bar charts should be separately prepared.

If no prescription is available on the day of each evaluation timepoint of the treatment period, the dose should be based on the immediately before prescription.

## 3) Analysis of previous ESA formulation by type

An analysis similar to “1) Study drug dosage” should be conducted by the type of previous ESA formulation (epoetin alfa or epoetin beta, darbepoetin alfa, epoetin beta pegol).

Only Conversion, Conversion (Hb value  $\geq 11.0$  g/dL), and Conversion (Hb value  $< 11.0$  g/dL) cohorts will be analyzed.

## 4) Analysis of previous ESA formulation by type and dose

An analysis similar to “1) Study drug dosage” should be conducted for weekly dose (darbepoetin alfa, epoetin beta pegol:  $\geq 15$   $\mu$ g,  $< 15$   $\mu$ g; 2 categories) of previous ESA formulation by type (darbepoetin alfa, epoetin beta pegol). The number of patients classified by dose was set to be almost equal.

Only Conversion, Conversion (Hb value  $\geq 11.0$  g/dL), and Conversion (Hb value  $< 11.0$  g/dL) cohorts will be analyzed.

## (5) Total number of dosage adjustments

The total number of dose adjustments for each study visit period from the first day to Week 24 of the treatment period and the entire treatment period from the first day to Week 24 is calculated; The number of subjects and their proportions with a 95% confidence interval (Clopper–Pearson [Exact] method) should be shown. The number and proportion of subjects by total number of dose adjustments for each scheduled study visit period should be shown.

The number and proportion of subjects and the 95% confidence interval (Clopper-Pearson [Exact] method) should be provided for the proportion of subjects defined below in each period between scheduled study visits and during the entire period from the first day to Week 24 of the treatment period. If a subject is included in more than one definition, the subject should be counted in each definition.

✓ No dosage adjustment: No change

With dosage adjustment: dosage adjustment (Dosage adjustment), dosage increase (Increase), drug interruption (Interrupt)

Dosage adjustment (Dosage adjustment) should include the number of times of increase, decrease, or interruption, and should not count as the increase when it is resumed after interruption.

(6) Iron supplement dosage

The following should be provided according to the 3 categories of oral iron supplement, intravenous iron supplement, and iron supplement (any route).

Descriptive statistics of the mean dosage of iron supplement per month for each treatment group should be calculated for the screening period, and after the first day of the treatment period, in each period between scheduled study visits and during the entire treatment period from the first day to Week 24 of the treatment period.

Descriptive statistics of the change in the mean dose of iron supplement per month from the baseline (mean dose of iron during the screening period) should be calculated, after the first day of the treatment period, in each period between scheduled study visits and during the entire treatment period from the first day to Week 24 of the treatment period. Before and after comparison should be conducted for changes from baseline using the paired t-test

The dosage of iron supplement should be calculated using the dose as iron.

If no iron supplement is administered, the dose should be tabulated as 0 mg. Subjects who changed the administration route of an iron supplement during the treatment period and subjects who had never received an iron supplement during the treatment period should be excluded from the tabulation.

(7) Proportion of subjects receiving oral, intravenous, or iron supplement (any route)

The number, proportion, and 95% CI (Clopper-Pearson [Exact] method) for the proportion of subjects treated with oral, intravenous, or oral iron supplement (any route) should be provided by treatment group for screening period, and after the first day of the treatment period, in each period between scheduled study visits and during the entire treatment period from the first day to Week 24 of the treatment period. McNemar tests should be used to compare baseline values (proportion of subjects receiving iron supplements by the aforementioned route in screening period) with before and after each period between scheduled study visits.

Subjects who have not received an iron supplement are to be subjects who have never received an iron supplement during the applicable period, and subjects who have received an oral, intravenous, or (any route) iron supplement are to be subjects who have received an iron supplement at least once during the period.

(8) Proportion of subjects with serum ferritin values of  $\geq 100$  ng/mL or TSAT of  $\geq 20\%$ .

The number, proportion and 95% CI (Clopper-Pearson [exact] method) for the proportion of subjects with serum ferritin values of  $\geq 100$  ng/mL or TSAT of  $\geq 20\%$  should be provided at each evaluation time point of the treatment period. Before and after comparison should be conducted for changes between baseline and each period between scheduled study visits using the McNemar test.

(9) Changes and rate of changes in iron-related indices (serum iron, TIBC, TSAT, and serum ferritin levels) and hepcidin from the first day of the treatment period

Descriptive statistics should be prepared for measured values of iron-related measures (serum iron, TIBC, TSAT, and serum ferritin values) and hepcidin at each evaluation time point of the treatment period and their change and rate of changes from the first day of the treatment period. A paired t-test should be performed for before and after comparison of changes and rate of changes from the first day of the treatment period.

LSMean, its standard errors, and 2-sided 95% CI should be calculated for the change in iron-related measures (serum iron, TIBC, TSAT, and serum ferritin values) and hepcidin from the first day of the treatment period to each evaluation time point using the MMRM model (with compound symmetry [CS] for a covariance matrix within subject variance). Only the serum ferritin value at each evaluation time point of the treatment period should be analyzed similarly.

The time course diagram of changes in the iron-related measures (serum iron, TIBC, TSAT, and serum ferritin levels) and hepcidin from the first day of the treatment period to each evaluation time point should be prepared. The 95% CI of LSMean will be represented by an error bar. For only the serum ferritin value, a time course diagram should also be prepared for mean ferritin value at each evaluation time point of the treatment period. The 95% CI of the mean will be represented by an error bar.

The serum ferritin values should be shown as follows.

- ✓ The following scatter plot chart should be provided by treatment group. Linear regression should be performed to calculate the p-value and correlation coefficient of the test with zero slope as the null hypothesis.

x: Serum ferritin value at baseline

y: Serum ferritin value at Week 24 of the treatment period

- (10) Changes in hematocrit, red blood cell count, reticulocyte (number and rate), mean corpuscular volume, mean corpuscular hemoglobin, and EPO from the first day of the treatment period

Descriptive statistics of hematocrit, red blood cell count, reticulocyte (number and rate), mean corpuscular volume, mean corpuscular hemoglobin, and EPO should be calculated at each evaluation time point. In addition, the change from the first day of the treatment period should be obtained, and the descriptive statistics should be calculated. A paired t-test should be performed for before and after comparison of changes from the first day of the treatment period.

LSMean, its standard errors, and 2-sided 95% CI should be calculated for the change in hematocrit, red blood cell count, reticulocyte (number and rate), mean corpuscular volume, mean corpuscular hemoglobin, and EPO (MT-6548 group only) from the first day of the treatment period to each evaluation time point using the MMRM model (with compound symmetry [CS] for a covariance matrix within subject variance).

A histogram of EPO measurements should be prepared for evaluation time point at Week 24 of the treatment period.

- (11) Changes in systolic blood pressure, diastolic blood pressure, and blood glucose from the start of the treatment period, changes and the rate of change in lipid (total cholesterol, LDL-C, HDL-C, LDL-C / HDL-C ratio, triglycerides) from the first day of the treatment period

Systolic blood pressure, diastolic blood pressure, lipids (total cholesterol, LDL-C, HDL-C, LDL-C / HDL-C ratio, triglycerides), and blood glucose should be analyzed in the same manner as hematocrit, red blood cell count, and reticulocyte (count and rate) in the preceding section.

The change from the first day of the treatment period should be obtained, and the descriptive statistics should be calculated. A paired t-test should be performed for before and after comparison of changes from the first day of the treatment period. LSMean, standard error, and 2-sided 95% CI should be calculated using the MMRM model (with compound symmetry [CS] for a covariance matrix within subject variance).

The descriptive statistics should be similarly calculated on the proportion of change from the first day of the treatment period at each evaluation time point of the lipid (total cholesterol, LDL-C, HDL-C, LDL-C / HDL-C ratio, triglycerides), and LSMean, standard error, and 2-sided 95% CI should be calculated using the MMRM model (with compound symmetry [CS] for a covariance matrix within subject variance).

No analysis will be performed for each patient cohort.

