## 4.14 Iron supplement dosage

The dose of iron supplements is defined by the following formula.

Mean monthly dose of iron supplements during the screening period\* and each scheduled study visit period (tabulation period of iron supplements) =  $(\text{Daily dose based on the physician's prescription} \times \text{Period of administration [days] of the corresponding dose}^3 \text{ during the tabulation period of iron supplements}) / \text{Tabulation period of iron supplements (days)}^4 \times 30.4375^5$

\*: The number of days of the screening period is “First day of the treatment period – First day of the screening period”.

\*2: For each period between the scheduled study visits, the actual study visit dates are not considered, and this tabulation is fixed as follows:

- ✓ The first day of the treatment period to Week 2 of the treatment period: The first day of the treatment period (Day 1) to Day 14
- ✓ Week 2 of the treatment period to Week 4 of the treatment period: Day 15 to Day 28
- ✓ The same shall apply thereafter, and the final period between the scheduled study visits should be Week 20 to Week 24 of the treatment period: Day 141 to a blood sampling day for hematological tests at Week 24 of the treatment period. However, for subjects who discontinued their treatment, the final period between the scheduled study visits should be up to the day before discontinuation.

\*3: If there are multiple applicable doses, the sum of the calculated values for each dose should be used.

\*4: For subjects who discontinued their treatment, the final period between the scheduled study visits (days) should be the actual number of days until the day before discontinuation.

\*5: In this tabulation, 1 month is counted as 30.4375 days ( $365.25/12 = 30.4375$ ).

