## **7.3 Handling of efficacy endpoints if rescue therapy is performed**

If rescue therapy is performed, data from the day after rescue therapy should not be used for efficacy analysis.

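### The test of change in iron dose (SAP 8.5.2(6)) drops subjects who stop iron completely but keeps those who start, so it is biased towards an increase

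*SAP*

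**What the plan says.** SAP 8.5.2(6) reports iron in three categories: oral, intravenous and any route. For each it analyses the "change in the mean dose of iron supplement per month from the baseline (mean dose of iron during the screening period"), by visit interval and over the whole treatment period. On testing it says: "Before and after comparison should be conducted for changes from baseline using the paired t-test".

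Two rules then settle who is counted. The first is a scoring rule: "If no iron supplement is administered, the dose should be tabulated as 0 mg". The second is an exclusion. It removes "Subjects who changed the administration route of an iron supplement during the treatment period" and adds that "subjects who had never received an iron supplement during the treatment period should be excluded from the tabulation". Iron use in screening plays no part in either exclusion.

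The March 2019 errata correct the neighbouring item 8.5.2(5) but leave this rule alone. Protocol 10.1.2(7) plans only a mean weekly dose, with no change from screening and no test, so the point is not a departure from a protocol test.

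**The concern.** Whether a subject enters the test depends on what happened after baseline, and it depends on the outcome itself. Stopping iron entirely gives the largest decrease a subject can have, and that subject is dropped. The mirror-image increase, from no iron to some, is retained.

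Two misreadings are possible. If complete stoppers and starters balance, the test can report a rise in iron dose when there is none. If some subjects stop, nobody starts and continuing users are unchanged on average, a real fall appears as roughly no change. Complete stopping can occur: protocol 8.5.2 has iron managed from the first day of screening and allows it to be omitted for poor responders, including those with allergy or adverse reactions.

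Route changers are a separate matter. Dropping them can move the mean either way, and they are dropped even from the any-route category, where route is irrelevant to the total.

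**Working it through.** **Which subjects are kept.** I read the exclusion as covering the paired test, since both sit in the same item and no other population is named for the test.

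| Iron in screening | Iron in treatment | Change | Under 8.5.2(6) |
|---|---|---|---|
| Yes | None at any time | Below 0 | Dropped |
| No | Some | Above 0 | Kept |
| Yes | Some | Either sign | Kept, unless route changed |
| No | None | 0 | Dropped |

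**Direction.** Leave route changers aside and let the changes over all subjects sum to 0. Never-users contribute 0. The retained sum is therefore minus the stoppers' sum, which is positive once one subject stops completely. The retained mean is then above 0, with no assumption about size.

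**Inputs.** From the documents: 40 subjects (SAP 2.3), a two-sided 5% level (8.1.1) and a month of 30.4375 days (4.14). The plan states no figure for iron dose to reproduce. Iron-use counts, doses and stopping rates are not given and are assumed below.

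**Fixed counts.** Take S stoppers, S starters at the same dose, C continuing users with change 0, and the rest never on iron. The all-subject mean change is 0. Under the SAP rule n = S + C, the mean is dose × S/n, and t = √(S(n−1)/C), so the p-value does not depend on the dose. For S = 4 and C = 10, t = √(4×13/10) = 2.28 on 13 df, p = 0.040. At 100 mg/month per user:

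| S | C = 10: mean, p | C = 20: mean, p |
|---|---|---|
| 2 | +16.7, 0.17 | +9.1, 0.16 |
| 4 | +28.6, 0.040 | +16.7, 0.043 |
| 6 | +37.5, 0.009 | +23.1, 0.011 |
| 8 | +44.4, 0.002 | +28.6, 0.003 |

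**Random counts.** Let D = 100 mg/day × 30.4375 = 3,043.75 mg/month per user. A share p0 of subjects is on iron in screening. Of these a share a stops completely, and a share b = p0·a/(1−p0) of non-users starts, which makes the true mean change 0. The expected retained share is p0(1−a) + (1−p0)b = p0, and the expected retained total per subject is (1−p0)·b·D = p0·a·D. The expected tested mean is therefore a·D: +152, +304 and +609 mg/month for a = 5%, 10% and 20%.

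Rejection rates come from 20,000 simulated trials per setting. Continuing users' change is normal with mean 0 and SD 0.25D or 0.5D. A share r of treatment users is excluded as route changers, unrelated to their change. Each cell gives the percentage for SD 0.25D / 0.5D.

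| p0 | r | a = 0 | a = 5% | a = 10% | a = 20% |
|---|---|---|---|---|---|
| 50% | 0 | 4.8 / 5.1 | 7.1 / 6.8 | 14.8 / 11.0 | 41.7 / 28.8 |
| 50% | 10% | 4.8 / 5.0 | 6.3 / 6.6 | 12.6 / 10.6 | 36.9 / 25.7 |
| 50% | 20% | 5.0 / 5.3 | 5.8 / 6.0 | 10.9 / 9.6 | 31.2 / 23.2 |
| 30% | 0 | 5.0 / 4.7 | 4.8 / 5.4 | 7.8 / 8.4 | 20.5 / 17.3 |
| 30% | 20% | 5.1 / 4.9 | 4.6 / 5.6 | 6.1 / 7.0 | 15.1 / 14.6 |

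Over all settings the test on all FAS subjects rejects 3.4–5.1% of the time, and the test on subjects with iron in screening or treatment 3.8–5.4%.

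**The case against.** The consequence is limited. Iron dose is one of ten other endpoints in SAP 3.1.2, the sample size rests on Hb precision, and no primary result uses this p-value. SAP 8.5.2(7) keeps non-recipients and compares the proportion on iron with screening by McNemar tests, so complete stopping and starting show there. This stands, and it is why the point is modest. But 8.5.2(7) concerns proportions; 8.5.2(6) is the only before-after test of dose amount, and nothing in (7) corrects its mean, interval or p-value.

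The sizes are assumed. That also stands. Nothing in the documents supports 10–20% complete stopping, and the protocol's iron targets work against it. A wider spread shrinks the effect: with SD equal to D and no route changers, rejection is 5.6%, 8.3% and 15.7% at 5%, 10% and 20% stopping with half on iron, and 5.4%, 6.8% and 12.0% with 30% on iron. The effect does not vanish, and that SD would imply a negative treatment dose for about one continuing user in six (a normal change more than one SD below 0).

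The oral and intravenous categories are less clear-cut. The SAP does not say whether never receiving iron is judged within each category or over any route. On the second reading, a subject on oral iron in screening and only intravenous iron in treatment stays in the oral category with a full decrease. The unqualified claim is therefore about stopping all iron.

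The SAP may have intended to describe iron users only. That is reasonable, but users then have to be defined by screening or treatment use, not by treatment use alone.

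**Conclusion.** The concern holds. The exclusion selects on the outcome in one direction, and no other section or erratum repairs it. The direction follows from the wording alone, route changers aside. The size depends on how many subjects stop completely: none if nobody does, little at 5%, and clear at 10% or more with half on iron if continuing users' changes have an SD of 25–50% of the dose.

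Three limits apply. One dose of iron during treatment keeps a subject in. Partial stoppers stay in, at 0 mg for the intervals without iron. The damage is confined to one supportive endpoint. It should be corrected because the rule is wrong as written and cheap to change; the Hb conclusions are not at risk.

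**What to change.** Replace the exclusion sentence in SAP 8.5.2(6) with wording such as:

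> The change from screening and its paired test include all FAS subjects, with 0 mg for any observed interval without iron. Intervals end the day before discontinuation (4.14), and data from the day after rescue therapy are not used (7.3). Subjects who change route remain in the any-route category. A table limited to subjects who took iron during treatment is descriptive, without a test.

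If a user population is preferred, the smaller edit is to exclude only subjects with no iron in either screening or treatment, and to keep route changers in the any-route category. This also removes the one-sided selection. Either way, state whether iron use is judged within each category or over any route. If route changers stay out of the oral and intravenous categories, report how many are excluded.

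The cost is SAP wording and a rerun of one table. Protocol 8.5.4 already has iron use recorded for both screening and treatment. The all-FAS version gives a lower mean dose with more zeros; the screening-or-treatment set avoids the never-users' zeros. If the data are already locked, protocol 13.4 allows the analysis to be added, with the reason given and the result kept distinct from the original plan.

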#### (12) QOL indices (EQ-5D-5L, KDQOL)

##### 1) EQ-5D-5L

The number, proportion, and 2-sided 95% CI (Clopper-Pearson [Exact] method) of subjects in responses in 5 levels to the 5 questions (mobility, self care, usual activities, pain / discomfort, anxiety / depression) should be provided at each evaluation time point.

For Index value and VAS score, descriptive statistics of measured values and descriptive statistics of changes from the first day of the treatment period should be provided at each evaluation time point. A paired t-test should be performed for before and after comparison of changes from the first day of the treatment period.

LSMean, its standard error, and 2-sided 95% CI should be calculated for the changes in Index value and VAS score from the first day of the treatment period at each evaluation time point using the MMRM model (with compound symmetry [CS] for a covariance matrix within subject variance).

